1 BACKGROUND AND RATIONALE

1.1 MBI as a Supplemental Screening Test

Approximately 40-50% of women presenting for screening mammography have mammographically dense breasts, a factor that severely limits sensitivity of the test. Molecular breast imaging (MBI) is one option offered for supplemental screening of dense breasts. As MBI is a functional imaging technique that relies on differences in preferential uptake of Tc-99m sestamibi in metabolically-active cells, it is able to reveal cancers hidden among dense fibroglandular tissue on a mammogram. Performing MBI after a negative mammogram in women with dense breasts detects an additional 7.7 to 8.8 breast cancers per 1000 women screened [1-3].

MBI is a nuclear medicine test that uses a high-resolution, semiconductor-based gamma camera to image the uptake of a radiotracer, typically Tc-99m sestamibi, in the breast. Mayo Clinic investigators have pioneered current MBI techniques and developed a low-radiation-dose MBI protocol for clinical use [4, 5]. Recently, MBI has been implemented across the multi-site Mayo Clinic practice.

1.2 Background Parenchymal Uptake (BPU) on MBI

In addition to detecting breast cancer, MBI also depicts the level of Tc-99m sestamibi uptake in non-cancerous fibroglandular tissue, termed background parenchymal uptake (BPU). BPU is subjectively assessed according to a validated lexicon as one of four categories (photopenic, minimal to mild, moderate, and marked) that describe the relative intensity of uptake in fibroglandular tissue[6]. A quantitative measure of BPU is also currently under development by [name] team (R21 CA197752). BPU varies among women with similar-levels of mammographic density and is associated with hormonal factors such as menopausal status and use of postmenopausal hormone therapy (Fig. 1) [7]. Importantly, we recently showed BPU associated with breast cancer risk; women with moderate or marked BPU have 3.4 to 4.8-fold increased risk compared to women with photopenic or minimal-mild BPU [8].

The exact mechanism of uptake of Tc-99m sestamibi in breast tissue is not entirely understood, but has been correlated with blood flow, tissue viability, mitochondrial activity, and mitotic activity in breast cancers. In an effort to understand histological characteristics that may account for variability in BPU, analysis has been performed on core biopsy specimens from 48 volunteers with mammographically dense breasts who have one of the extreme BPU categories of either photopenic BPU (N = 28) or marked BPU (N

Fig. 1 Examples of background parenchymal uptake categories. Molecular breast imaging (MBI) examinations and corresponding full-field digital mammograms from four different women are shown. All images were acquired in the mediolateral oblique projection. MBI with photopenic background parenchymal uptake е (BPU) (a) and corresponding mammogram (b). MBI with minimal to mild BPU (c) and corresponding mammogram (d). MBI with moderate BPU (e) and corresponding mammogram (f). MBI with marked BPU (g) and corresponding mammogram (h)

= 20) on MBI (unpublished data). BPU was associated with differences in tissue composition: specimens with marked BPU comprised a higher proportion of epithelial cells (22% vs. 2.8%, p<0.0001) and a lower proportion of stroma (47% vs. 75%, p = 0.005).

BPU was inversely correlated with lobular involution status and associated with Ki-67 positivity (8.6% positive in marked BPU vs. 2.6% positive in photopenic BPU, p = 0.006). These associations with histologic features further support a relationship between BPU and breast cancer risk.

We hypothesize that BPU is positioned to serve as a functional imaging biomarker to identify the subset of women with dense breasts who are at greatest breast cancer risk and most likely to benefit from tailored screening or preventive options. However, more study is needed to understand BPU as a marker of risk. It is yet unclear how BPU changes over the course of a woman's lifetime and whether these changes are related to changes in breast cancer risk. Further, it is unknown whether chemopreventive options such as tamoxifen would decrease BPU and whether these changes could serve as a surrogate marker for decrease in risk.

1.3 Low-dose Tamoxifen

Tamoxifen is a selective estrogen receptor modulator (SERM) that blocks the effects of estrogen on breast tissue. Tamoxifen is FDA-approved as a chemopreventive option for both premenopausal and postmenopausal women. Studies have shown that preventive tamoxifen, when taken daily for five years, can reduce risk of developing breast cancer by at least one-third. Results from the National Surgical Adjuvant Breast and Bowel Project showed that in women considered at increased risk for breast cancer, preventive tamoxifen reduced breast cancer risk by approximately one-half [9]. However, at the standard clinical dose of 20 mg per day, tamoxifen can produce side effects such as menopausal symptoms, and also carries a small risk (<1% of participants) of serious adverse events, including uterine cancer and blood clots in legs or lungs. Concerns about the risk of these adverse events accounts for overall low utilization of tamoxifen for chemoprevention. In patients who do start tamoxifen, side effects of the drug can lead to non-compliance with long-term use.

Because of these concerns, multiple investigations have been done to determine efficacy of tamoxifen at lower doses. Tamoxifen taken at 5 mg per day has been proposed as an optimal dosage that is associated with decreasing biomarkers of breast disease (including mammographic density), and reduced breast cancer risk while potentially mitigating the adverse events and side effects seen at the 20 mg/day dose [10-12]. Other studies have evaluated efficacy of tamoxifen at 10 mg/day [13-15]. In one study conducted among women being treated for breast cancer, tamoxifen at 10 mg per day over a short period of 14 days resulted in clinically and statistically meaningful declines in molecular markers of estrogen receptor positivity, progesterone receptor positivity and Ki-67 (a marker of cellular proliferation) [15].

1.4 Study Purpose

In this study, we aim to determine whether short-term intervention with low-dose tamoxifen can induce a decline in BPU. Results from this study will provide critical knowledge on factors that influence changes in BPU and inform future study of BPU as a modifiable risk factor.

2 STUDY OBJECTIVE

To assess changes in background parenchymal uptake (BPU) on MBI before and after low-dose tamoxifen intervention (5 mg per day for 30 days or 10 mg per day for 30 days), among women with a history of high BPU. It is hypothesized that both subjective categorical and quantitative measures of BPU will decline with low-dose tamoxifen intervention.

3 STUDY DESIGN

We propose a prospective clinical trial to be conducted within our cohort of women who have previously had an MBI test performed at Mayo Clinic. In this study, women with high

BPU on MBI will be invited to participate in a short-term intervention of low-dose tamoxifen (5 mg per day for 30 days or 10 mg per day for 30 days). MBI will be repeated at the end of the intervention. Change in BPU before and after the intervention will be assessed with both subjective and quantitative measures.

4 SELECTION AND ENROLLMENT OF PARTICIPANTS

The study population will include women who have no history of breast cancer and have previously had an MBI showing high BPU.

4.1 Inclusion Criteria

The following are requirements for entry into the study:

- 1) Female, age 40 or older at the time of enrollment
- 2) Most recent MBI examination, performed within 3 years of enrollment, showed moderate or marked background parenchymal uptake
- 3) Mammogram performed within 24 months prior to enrollment that is available for comparison
- 4) Willing and able to return for MBI following 30 days of low-dose tamoxifen
- 5) If able to become pregnant
 - a. Negative pregnancy test within 48 hours prior to study MBI exam(s)
 - b. Agrees to avoid pregnancy during the study and for at least 2 months after study participation ends, by abstinence, barrier method, or nonhormonal contraception.
- 6) Understands and signs the consent form

4.2 Exclusion Criteria

Subjects will be excluded if any of the following characteristics are present:

- 1) Evidence of suspected breast disease as defined by positive findings or recommendation for short-interval follow-up on most recent breast imaging (including mammography, MBI, MRI, ultrasound, etc.) not yet resolved prior to enrollment
- 2) Breast biopsy or breast surgery performed within 6 months prior to enrollment
- 3) Bilateral breast implants or status post-bilateral prophylactic mastectomy
- 4) Pregnant or lactating
- 5) Current or recent use (within 6 months prior to enrollment) of any of the following drugs:
 - a. Systemic hormonal therapy (oral or transdermal patch formulations)
 - b. Hormonal contraception (oral, transdermal, implanted, or injected formulations not allowed, however hormonal IUDs are acceptable)
 - c. Selective estrogen receptor modulators (tamoxifen, raloxifene, or toremifene)
 - d. Aromatase inhibitors (anastrazole, letrozole, or exemestane)
 - e. GnRH analogs
 - f. Prolactin inhibitors
 - g. Androgens or antiandrogens

- h. Anticoagulants or "blood thinners" (warfarin, heparin, rivaroxaban and other novel anticoagulants)
- i. Drugs known to be strong inhibitors of CYP2D6, the major P450 enzyme that metabolizes tamoxifen, including:
 - bupropion (Wellbutrin)
 - fluoxetine (Prozac)
 - paroxetine (Paxil)
 - quinidine (Quinidex)
- 6) Personal history of any type of malignancy, with the exclusion of non-melanoma skin cancer, diagnosed prior to enrollment
- 7) Personal history or strong family history of blood clots in legs or lungs (also known as deep vein thrombosis or pulmonary embolism)
- 8) Personal history of transient ischemic attack (TIA) or cerebrovascular accident (CVA)
- 9) Active proliferative disorders of the endometrium such as atypical hyperplasia, history of active endometriosis, unresected polyps
- 10) Any type of retinal disorders or severe cataract
- 11) Current smoker
- 12) Known carrier of BRCA1 or BRCA2 genetic mutation or known DNA repair defect.
- 13) Blood pressure above 140/90

4.3 Enrollment Procedures

Our Mayo Clinic MBI databases will be reviewed to identify potential candidates for this study. Women who have had high (moderate or marked BPU) on a prior MBI study, performed within 3 years of enrollment in the current study, with no apparent conflict with inclusion and exclusion criteria will be contacted by invitation letter. This letter informs patients of our new research findings showing the association between high BPU and breast cancer risk and offers study participation. Patients may contact the study team by phone or email. The study coordinator will assess patient eligibility, discuss study procedures with the patient, and schedule an in-person enrollment visit at which informed written consent will be obtained. The physician co-principal investigator of the study will be available for consultation during the consent process.

5 STUDY PROCEDURES

5.1 Schedule of Evaluations

Potential participants will be screened for eligibility and undergo informed written consent with the study coordinator at the time of enrollment. At Study Visit 1, the participant will be asked to complete a study questionnaire and undergo MBI (after a negative pregnancy test as necessary). Participants will then undergo 30 days of low-dose tamoxifen medication followed by Study Visit 2, at which time a repeat MBI test will be performed.

	Enrollment	Study Visit 1	30 days between visits	Study Visit 2
Eligibility Checklist	X			
Informed Consent	X			
Questionnaire: Breast Health and History		Χ		
Blood pressure measurement		X		
Urine pregnancy test (if necessary)		Х		Х
MBI		Χ		X
Tamoxifen (5 mg/day for 30 days or 10 mg/day for 30 days)			X	
Check-in phone calls at day 5 and 20			Х	
Study close-out				X

5.2 Pregnancy test

All participants who can become pregnant will be required to have a urine pregnancy test performed with negative results within 48 hours prior to each MBI injection. The study coordinator will administer this test.

5.3 Blood pressure test

Participants will undergo a blood pressure test prior to starting low-dose tamoxifen. The study coordinator will administer this test with an automated machine. If a participant has blood pressure over 140/90, she will not proceed with the study.

5.4 Molecular breast imaging (MBI)

MBI testing will be performed at Mayo Clinic Rochester within the Division of Breast Imaging and Intervention. MBI procedures will be done as per clinical standard of care (described below).

- 5.4.1 Equipment MBI examinations will be performed on an FDA-approved dual-head gamma camera system comprised of cadmium zinc telluride detectors and collimation optimized for low-dose breast imaging (LumaGem, Gamma Medica, Salem, NH).
- 5.4.2 Technologists Radiotracer injection and MBI image acquisition shall be performed by female nuclear medicine technologists who have received training in mammographic positioning techniques.
- 5.4.3 Patient preparation Patients will be asked to fast for a minimum of 3 hours prior to the MBI examination, when possible, as prior studies have shown fasting to improve uptake of Tc-99m sestamibi in breast tissue by reducing splanchnic and hepatic blood flow.[16] Patients may take fluids, including black coffee, tea, diet soda and water.

Patients will remove all clothing and jewelry above the waist and put on a patient gown. Patients may be given a warm blanket to wrap around their shoulders and chest prior to

the MBI examination, in order to increase peripheral blood flow to breast tissue and thus improve Tc-99m sestamibi uptake.

5.4.4 Tc-99m sestamibi injection - The technologist should verify that the patient is not pregnant or breast feeding prior to injection of Tc-99m sestamibi.

MBI examinations will be performed with a dispensed dose of 8 mCi (300 MBq) Tc-99m sestamibi (range 7.2 - 8.8 mCi). A nuclear medicine technologist will deliver an intravenous injection of the Tc-99m sestamibi dose in an antecubital vein of either arm. Flushing of the syringe with saline and use of syringes that provide low sestamibi adhesion is recommended to minimize residual activity.

Infiltration, or extravasation of the injected dose into the soft tissue rarely occurs (~1-2% of studies). If infiltration is suspected, the technologist will observe the count rate obtained on a persistence view prior to beginning imaging. If the count rate is lower than typical (defined as less than 0.2 kcts/minute in the craniocaudal [CC] view and less than 0.3 kCts/minute in the mediolateral oblique [MLO] view for an average-sized breast) the technologist will image the injection site to evaluate.

If there is no evidence of infiltration on imaging of the injection site, the technologist will proceed with the breast images. If infiltration is confirmed by both low count rates and high uptake at the injection site, the technologist will ask for the patient's consent to proceed with a second injection of 8 mCi Tc-99m sestamibi. The patient will be given the option to refuse a second dose and continue with the study, although poor image quality may be obtained, or to discontinue MBI imaging and thus end study participation.

5.4.5 Image acquisition - MBI imaging will commence immediately after injection. Two views of each breast will be acquired in the CC and MLO projections. Acquisition duration will be 10 minutes per view. Images will be acquired in static mode using an energy acceptance window of 110-154 keV.

For each view, patients will be seated with the breast positioned between the two detectors. The persistence-scope should be used to validate correct breast positioning. If available, the recent mammogram can be viewed to replicate positioning on the MBI. Light compression is applied to stabilize the breast and to limit motion artifact. Placement of pillows behind the patient's back is recommended to reduce motion and increase comfort. Verification of the patient's comfort level and ability to complete 10 minutes of imaging in the position should be done before acquisition begins. Compression thickness for each MBI view will be recorded. At Study visit 2, the compression thickness for each view will be adjusted to match that recorded from the Study visit 1.

In participants with breasts larger than the detector field of view, the technologist may opt to acquire two 10-minute tiled MLO views of each breast, in place of a CC and MLO view, in order to ensure that the entire breast is included in the image set.

During the acquisition of each view, the technologist will briefly place the appropriate Co-57 laterality markers (R for right and L for left) in the field of view until well seen on the persistence screen.

The patient will be visually monitored by the nuclear medicine technologist from the time of injection of the radionuclide until image acquisition is completed.

5.4.6 Post-acquisition processing - Following completion of the acquisition, the technologist will format the acquired images in the standard format used for MBI display and interpretation.

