5.7 Image Analysis

Quantitative assessments of BPU on all MBI studies will be performed by study staff using region of interest analysis. Counts within breast fibroglandular tissue and areas of fat in the breast will be obtained to calculate the ratio of counts per pixel in fibroglandular tissue vs. fat. Change in this ratio across MBI studies performed within patients will be determined.

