9 SAMPLE SIZE CONSIDERATIONS

There have yet to be any studies examining BPU response to tamoxifen. Thus, this study is a pilot design that will aim to enroll 30 patients who complete pre- and post-tamoxifen MBI. A sample size of 30 will have 80% power to detect a means change of 1 BPU quantitative unit (e.g. overall mean of 4.5 pre low-dose tamoxifen intervention, and post tamoxifen mean of 3.5), assuming a standard deviation of differences of 1.89 (effect size = 0.53), using a paired t-test with an α =0.05 two-sided significance level.

Allowing for potential study withdrawals, we will allow for a total of 50 patients to begin the low-dose tamoxifen intervention. In addition, women who are invited to participate may not have persistent BPU on their MBI performed at Study Visit 1. Prior pilot data showed that approximately half of women with prior high BPU had persistent high BPU on a current MBI. Therefore, up to 100 women will be screened with MBI to assess potential enrollment in the low-dose tamoxifen intervention. We will aim to balance enrollment of premenopausal and postmenopausal subjects.

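### Fasting and warm-blanket use, which the protocol says improve tracer uptake, are not recorded at either scan, and blanket use is not matched between a woman's two scans

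*Combined protocol and SAP*

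**What the plan says.** Section 5.4.3 covers preparation for every MBI. On fasting: "Patients will be asked to fast for a minimum of 3 hours prior to the MBI examination, when possible". The reason given is that earlier studies found fasting to improve sestamibi uptake in the breast. On warmth: "Patients may be given a warm blanket to wrap around their shoulders and chest prior to" the scan, "in order to increase peripheral blood flow to breast tissue and thus improve Tc-99m sestamibi uptake". So fasting is a standing request with room for exceptions, and the blanket is optional each time.

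No section asks staff to note whether a woman fasted or had a blanket. In the schedule (section 5.1) the questionnaire appears at Visit 1 only and concerns breast health and history. The drug diary (section 5.6) covers doses and symptoms.

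Section 5.4.5 treats another acquisition factor differently. Compression thickness is recorded for each view, and "At Study visit 2, the compression thickness for each view will be adjusted to match that recorded from the Study visit 1".

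The quantitative outcome (section 5.7) uses region-of-interest counts "to calculate the ratio of counts per pixel in fibroglandular tissue vs. fat" and takes the within-patient change in that ratio. The BPU categories (section 1.2) "describe the relative intensity of uptake in fibroglandular tissue". Section 9 plans 30 completers, a change of 1 unit and a two-sided paired t-test at 0.05, "assuming a standard deviation of differences of 1.89".

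**The concern.** In a before-and-after design, anything that changes the measurement between the two scans enters the outcome directly. Here the protocol itself names two such factors for uptake, leaves both variable, and keeps no record of them. If they vary haphazardly between a woman's scans, they widen the spread of the changes. If they vary systematically by visit, for example because blankets are offered more often at one visit than at the other, they move the mean change. Both arms take tamoxifen (section 5.6), so no untreated group would reveal such a shift. Blinding readers to scan order (section 5.5) protects the reading, not the acquisition. Without a record, nobody could check afterwards whether preparation differed.

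**Working it through.** **1. The plan's own figure.** Inputs from section 9: n = 30, mean change 1, SD of differences 1.89, two-sided alpha 0.05. Effect size = 1/1.89 = 0.529. Exact paired-t power (noncentral t, 29 df, noncentrality 0.529 × √30) is 79.98%, which agrees with the stated 80%.

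**2. Does preparation reach the outcome?** If a step multiplies gland counts by a and fat counts by b, the ratio becomes (a/b) × the old ratio. When a = b it cancels exactly. Only a differential effect survives. The documents do not say whether a and b differ.

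**3. If the noise is already inside 1.89.** Let *share* be the assumed part of the variance of differences due to preparation. Total variance = 1.89² = 3.572. Removing all of it leaves SD = √(3.572 × (1 − share)).

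| Assumed share | Remaining SD | Power at n = 30 |
|---|---|---|
| 0% | 1.89 | 80.0% |
| 5% | 1.84 | 82.0% |
| 9.3% | 1.80 | 83.7% |
| 19.1% | 1.70 | 87.6% |

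In this case planned power is correct as it stands, and the table shows a possible gain, not a shortfall.

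**4. If the noise lies outside 1.89.** For an assumed extra SD s of the change, SD = √(1.89² + s²).

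| Assumed s (units) | SD | Power at n = 30 |
|---|---|---|
| 0.25 | 1.906 | 79.3% |
| 0.50 | 1.955 | 77.3% |
| 0.75 | 2.033 | 74.0% |
| 1.00 | 2.138 | 69.7% |

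**5. What such values would require.** Suppose one step shifts the ratio by e units and is applied independently at each scan with probability q. The added variance of the change is 2q(1 − q)e².

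- e = 0.5, q = 0.8: variance 0.08, s = 0.28, power 79.1%.
- e = 1.0, q = 0.8: variance 0.32, s = 0.57, power 76.5%.
- e = 1.0, q = 0.5: variance 0.50, s = 0.71, power 74.6%.

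Against the example mean of 4.5 in section 9, e = 0.5 is an 11% differential effect (0.5/4.5) and e = 1.0 is 22%. The 19.1% share in step 3 equals a variance of 0.682. A single step at q = 0.5, where the added variance is largest, would need e = √(0.682/0.5) = 1.17 units, more than the 1-unit change the trial is designed to detect. The top of the range is therefore generous for any one step.

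**6. Systematic difference.** If the step is used with probability q1 at Visit 1 and q2 at Visit 2, the mean change shifts by (q1 − q2) × e. With assumed values 0.8, 0.5 and 0.5 units, that is 0.3 × 0.5 = 0.15 units towards an apparent fall; reversing the visits reverses the sign.

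**The case against.** The strongest reply is that the outcome is largely protected already. One site uses one preparation section for every scan, and the fasting request is the same each time, so only compliance can differ. Section 5.4.3 explains both steps through blood flow, which suggests tracer delivery to the breast as a whole, and a gland-to-fat ratio removes a proportional change. The documents give no figure for any residual effect, so every magnitude above rests on assumed inputs. The remedy also does not match fasting, so the gain to 88% is out of its reach.

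Most of this stands. It limits the size of the point, but it does not answer the omission. Cancellation is plausible but not shown. Exceptions to fasting go unrecorded, and the blanket is a free choice at each scan. The protocol has already accepted the principle by matching compression thickness.

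Three stronger readings are tempting and are not supported:

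- A reader might infer that the trial is underpowered. The source of 1.89 is not given and it may already contain ordinary preparation variation, in which case the 80% stands.
- A reader might infer that uneven preparation explains a fall in BPU through regression to the mean, since section 9 implies that Visit 1 BPU screens women for treatment. The documents do not support attributing such a fall to preparation. Other within-woman variation would also contribute, and this fix leaves that untouched.
- A reader might add the optional tiled views for large breasts as a further unmatched factor. Matching thickness view by view already presupposes the same views at both visits.

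**Conclusion.** The point holds as a modest one. Two factors that the protocol says affect uptake are unrecorded, and one of them, the blanket, is left to discretion at each scan without matching, in an uncontrolled within-woman comparison. The consequence is possible avoidable noise, or a possible shift if use differs by visit. Its size cannot be derived from the documents and may be near zero. Under assumed shares of 0% to 19% of the variance of differences, removing all preparation noise would give power between 80% and 88%; this is an upper bound that the fix would not fully reach. If the noise lies outside 1.89, an added SD of up to 0.5 units costs under 3 percentage points of power, and 1.0 unit costs about 10. Nothing here shows that the stated 80% is wrong or that an observed decline would be an artefact. The change is worth making because it is nearly free and because preparation cannot be reliably reconstructed once the scans are done.

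**What to change.** Extend the matching sentence in section 5.4.5, with a cross-reference from 5.4.3: *Fasting status (at least 3 hours, yes/no) and warm-blanket use will be recorded at each study MBI, and warm-blanket use at Study Visit 2 will match Study Visit 1.*

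Leave the fasting request unchanged at both visits, so that no woman is asked to repeat an unfasted scan. Keep all pairs in the main analysis. Report how many pairs had the same fasting status and, optionally, the mean change with its confidence interval in those pairs, as a descriptive check and not a test. At SD 1.89 the 95% half-width, t × 1.89/√n, is 0.71 units with 30 pairs, 0.78 with 25 and 0.88 with 20.

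The cost is one line on the technologist's worksheet, with no extra scans, staff or patients. The limitation is that noise from fasting is described, not removed.

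### Section 5.4.5 matches Visit 2 to Visit 1 explicitly only on compression thickness; the woman's own Visit 1 MBI would be a better positioning reference than an optional mammogram

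*Combined protocol and SAP*

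**What the plan says.** All of the following is in the combined protocol and SAP.

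- **Held the same at both scans (5.4 to 5.4.5).** One site, one camera system, a dispensed dose of 8 mCi (range 7.2 to 8.8), and a 110-154 keV energy window. Each view lasts 10 minutes, and the default is one CC plus one MLO view per breast. The start is fixed as well: "MBI imaging will commence immediately after injection".
- **Matched from Visit 2 back to Visit 1 (5.4.5).** One item: "At Study visit 2, the compression thickness for each view will be adjusted to match that recorded from the Study visit 1".
- **Positioning (5.4.5).** "If available, the recent mammogram can be viewed to replicate positioning on the MBI". There is also a live check: "The persistence-scope should be used to validate correct breast positioning". Neither refers to the Visit 1 MBI.
- **The mammogram (4.1, inclusion 3).** "Mammogram performed within 24 months prior to enrollment that is available for comparison".
- **View set (5.4.5).** For breasts larger than the detector field, the technologist may replace the CC and MLO views with two tiled MLO views. The choice at Visit 2 is not tied to the choice at Visit 1. No order of views or breasts is given.
- **Outcome (5.7).** A region-of-interest ratio of counts per pixel in fibroglandular tissue to those in fat. "Change in this ratio across MBI studies performed within patients will be determined".

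**The concern.** The plan already accepts that Visit 2 acquisition should copy Visit 1, because it records compression thickness and reproduces it. It does not extend that principle to positioning, where it points to a different image.

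In a planar projection, the rotation of the breast and the amount brought onto the detector affect which tissue lies in the fibroglandular and fat regions. Matching thickness does not control this. The Visit 1 MBI is the natural template. It has the same modality, camera system and default projections, it is about 30 days old (less if a woman stops tamoxifen early), and it is in hand for everyone at Visit 2.

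What is at stake is precision. Positioning differences between the two scans add to the standard deviation of the differences, the quantity on which the section 9 power statement rests. Neither arm is untreated, so the trial has no internal measure of how much scan-to-scan variation comes from repositioning alone.

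**Working it through.** **1. What is matched, item by item**

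| Feature | Same rule at both visits | Visit 2 told to copy Visit 1 |
|---|---|---|
| Site, camera system | yes | not needed |
| Dose range, immediate start | yes | not needed |
| Duration, energy window | yes | not needed |
| Compression thickness | – | yes |
| Breast positioning | persistence-scope check; mammogram optional | no |
| View set (CC/MLO or tiled MLO) | default CC/MLO, tiling at technologist's option | no |
| View order | not stated | no |

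**2. Reproducing the plan's figure.** Inputs from section 9: n = 30, mean change 1, SD of differences 1.89, paired t-test, two-sided α = 0.05.

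- Effect size = 1 / 1.89 = 0.529 (stated 0.53).
- Noncentrality = √30 × 1 / 1.89 = 2.898, with 29 degrees of freedom.
- Power from the noncentral t = 79.98% (stated 80%). It reproduces.

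**3. Illustration A: the noise is already inside the 1.89 and matching removes it.** Let f be the assumed share of the variance of the differences that is avoidable. The documents give no value for f. The reduced SD is 1.89 × √(1 − f).

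| f | SD | Noncentrality √30 / SD | Power at n = 30 |
|---|---|---|---|
| 5% | 1.842 | 2.973 | 82% |
| 10% | 1.793 | 3.055 | 84% |
| 20% | 1.690 | 3.240 | 88% |

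**4. Illustration B: the noise comes on top of the 1.89.** For an assumed extra per-scan SD of s, the SD of differences becomes √(1.89² + 2s²).

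| s (BPU units) | SD | Power at n = 30 |
|---|---|---|
| 0.25 | 1.923 | 79% |
| 0.50 | 2.018 | 75% |
| 0.75 | 2.167 | 69% |

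Section 9 does not give the source of 1.89, so the documents cannot decide between A and B or supply f or s. Both tables show sensitivity to assumptions and are not estimates.

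**5. Direction.** If repositioning error is unsystematic, its expected contribution to the mean difference is zero. It widens the interval and leaves the mean change unbiased.

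**The case against.** **Much is already standardised.** The fixed settings, technologists trained in mammographic positioning and the persistence-scope check make the two scans broadly alike. This stands, and the point is limited to explicit matching of Visit 2 to Visit 1. Thickness matching view by view also implies the same views at both visits, but nothing requires this when tiling is an option.

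**The mammogram can serve as a common template.** A reader might infer that a reference up to 24 months old undermines the comparison. The documents do not support that. Twenty-four months is an upper limit at enrollment, inclusion 3 requires an available mammogram, and if the same one is viewed at both visits its age matters little. What remains is that viewing it is optional and that it comes from another modality.

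**Power.** A reader might infer that the trial is underpowered. It is not shown to be: the stated figure reproduces, and 1.89 may already contain ordinary repositioning noise. Section 9 also speaks of a BPU quantitative unit without identifying it as the 5.7 ratio. That link is an inference, although the ratio is the only quantitative measure the protocol defines.

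**View order.** A reader might infer that unfixed order distorts the change, since four 10-minute views spread imaging over about 40 minutes. This needs an assumed drift in the ratio and assumed random ordering, and the documents report neither. A within-image ratio also cancels decay and overall count-rate changes. Even granting independent random order at both visits and a drift of 5% to 20% of a mean of 4.5 from first to last view, the effect is small. The per-slot shift is 4.5d/3 and the slot-difference variance is 2 × 1.25 = 2.5. The added SD for a single view is therefore 0.12 to 0.47, or 0.4% to 6% of 1.89². It would largely cancel if all four views were averaged, which 5.7 does not specify. View order is therefore a minor point.

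**Conclusion.** The point holds as an inexpensive improvement to the design. Section 5.4.5 names an optional reference from another modality for positioning when a closer one, the Visit 1 MBI, exists for every woman at Visit 2. It also leaves the tiled-MLO choice free to differ between visits. The consequence is some avoidable loss of precision in the within-woman change in BPU.

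The size is unknown, because the documents contain no scan-to-scan repeatability figure. The rise from 80% to 82–88% power rests entirely on the assumption that 5% to 20% of the variance of the differences is avoidable and already included in 1.89. No bias in the mean change and no error in the sample-size statement has been shown.

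**What to change.** Keep the mammogram as the positioning reference for Visit 1. Next to the compression-thickness rule in 5.4.5, add:

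> At Study Visit 2 the participant's Study Visit 1 MBI will be displayed, and each view will be positioned to reproduce it, using the same view set (CC/MLO or tiled MLO) and the same view order.

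The view-order clause is the least important part. To make it workable, the view set and order should be recorded at Visit 1 alongside the thickness.

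Cost: one sentence and slight extra technologist time at Visit 2, with no extra scan, radiation or participants. The technologist will know that it is the second scan, but the thickness-matching rule already reveals that. The order-blinding of the radiologists' assessment in 5.5 need not change.
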